Effectiveness of a Culturally Adapted Cognitive Behavioral Intervention to Reduce Psychological Distress and Improving Well-Being Among University Students During the COVID-19 Pandemic

[NCT ID not yet assigned]

21.03.2021

The Study Protocol

The proposed project aims to conduct a study in which a culturally adapted cognitive behavioral intervention (CA-CBI) will be implemented in an online group format to prevent the expected psychological problems, reduce psychological distress and increase the well-being of the university students and effectiveness of this intervention will be measured. In this regard, a survey study and a diagnostic interview will be conducted to detect the distress and whether the individual has any psychological problem severe enough to meet the diagnostic criteria (for screening purposes; the ones who do not have a considerable amount of distress and who have a diagnosis would not be included in the study), depression, anxiety, traumatic stress and well-being levels of the participants in addition to the COVID-19 related factors and demographic variables. In the intervention part, CA-CBI will be implemented in a group format on Zoom which is an online platform with HIPAA compliance. For this purpose, the CA-CBI manual will be adapted to the sample of university students and the problems they are experiencing during the COVID-19 pandemic. Then, psychological problems and the well-being of the participants will be measured three times (one week before the intervention, one week after the intervention and one month after the post-measurement) to evaluate the efficacy, and a process evaluation will be made to evaluate the feasibility of the intervention.

This project consists of 4 stages. In the first stage, the CA-CBI manual will be adapted for the sample of university students and the problems they are experiencing during the COVID-19 pandemic. For this purpose, the four steps of the DIME (design, implementation, monitoring and evaluation) methodology will be followed: a) Free-listing interviews, b) Key-informant interviews, c) Focus group interviews, and d) Cognitive interviews.

In the second stage, two surveys and a diagnostic interview will be conducted on the internet to learn about demographics, COVID-19 related data (precautions, exposure, etc.), psychological problems and the well-being. The first survey and diagnostic interview will be done by the screening purposes. They will first fill the Kessler Psychological Distress Scale (K10) as a first step of screening. The ones who score higher than 15 will and have no suicidality continue to the next screening phase which is conducting Structured Clinical Interview for DSM-5 (SCID-5). After conducting SCID-5, the ones who do not have a diagnosis for any type of psychiatric disorders according to DSM-5 will be included to the study and have the pre-test. Pre-test survey will take 20-25 minutes. The sample will consist the adult university students living in Turkey. It is aimed that 100 participants who meet the inclusion criteria would participate to this phase of the study (The data collection will stop when the aimed number of participants meeting the inclusion criteria is achieved). The links of the surveys which will be created on Qualtrics will be shared on social media and communication platforms. On these links, participants will first see the information about the study, and after giving consent to participate in the study, they will be able to complete the questionnaires.

In the third stage, the 8-week online group CA-CBI and its efficacy measurement will be conducted to test whether the CA-CBI works for the university students experiencing distress during the COVID-19 pandemic. Only the participants who meet the inclusion criteria, pass the screening procedure and approve to be part of the intervention will take place in this stage. The aimed participant number for this stage is 100. Participants will be randomly

assigned to the care as usual and care as usual/intervention groups. Control (care as usual) group will receive information about the freely available support options. Two other measurements will be taken about psychological problems and well-being at one week after the intervention (post-test) and one month after the post-test (follow-up). After all the measures are completed, the control group will be able to receive the intervention.

In the fourth stage, a process evaluation will be conducted to evaluate the feasibility of delivering CA-CBI to university students in an online group format. The process evaluation will consist of interviews in which participants will be asked about the facilitators and the barriers of attending/delivering the sessions. The participants of this process will be 5 completers, 5 drop-outs and 2 facilitators who apply CA-CBI.

The data will be analyzed by using a statistical package called IBM SPSS 26.0. The effectiveness of the intervention will be tested by comparing the changes in the scores of primary outcome measure (K10) and secondary outcome measures (PHQ-9, GAD-7, PCL-5, WHO-5) between the baseline and follow-up measure. Mediation analyses will be conducted to explore the mechanisms of change by using the Dispositional Hope Scale, Emotion Regulation Questionnaire and Acceptance and Action Questionnaire-II.

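### Does stopping recruitment at 100 eligible students leave fewer than 100 to randomise?

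*Protocol*

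**What the plan says.** The protocol is organised by stages rather than numbered sections. In the second stage, applicants complete the K10 and then, if they score above 15 without suicidality, the SCID-5. Those without a diagnosis "will be included to the study and have the pre-test". The size of this stage is set as follows: "It is aimed that 100 participants who meet the inclusion criteria would participate to this phase of the study". The stopping rule is added in parentheses: "The data collection will stop when the aimed number of participants meeting the inclusion criteria is achieved". The same paragraph describes the survey links. At the outset, "participants will first see the information about the study". Consent comes next, and the survey opens only then: "after giving consent to participate in the study, they will be able to complete the questionnaires".

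The third stage contains the random assignment. Its entry condition reads: "Only the participants who meet the inclusion criteria, pass the screening procedure and approve to be part of the intervention will take place in this" (the third stage). Its size is given next: "The aimed participant number for this stage is 100".

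**The concern.** The two stages carry the same target but do not list the same conditions. The second-stage stop is counted on eligibility. The third stage names eligibility, passed screening and approval of the intervention. If approval is a separate step taken after the count has closed, the most the second stage can supply is exactly what the third stage aims for, and one refusal gives at most 99. The protocol describes no over-recruitment, replacement of decliners or reopening of the survey links.

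At stake would be some precision, and a stated size that the stopping rule does not by itself secure. The validity of the comparison would not be at stake, because anyone who declines does so before being assigned to an arm.

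**Working it through.** **Inputs.** The second-stage aim and stop are 100 people meeting the inclusion criteria. The third-stage aim is 100. The protocol gives no acceptance rate, so the acceptance share *a* below is an assumption. The protocol shows no derivation of the figure 100 (no effect size, standard deviation, power or dropout rate), so there is no sample-size calculation to reproduce.

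**Size of the possible shortfall.** If the stop stays at 100 and approval is asked afterwards, the expected number randomised is 100 × *a*. To randomise 100 on average, the number of eligible people needed is 100 / *a*, rounded up.

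| Assumed *a* | Randomised, 100 × *a* | Eligible needed, 100 / *a* | Extra |
|---|---|---|---|
| 1.00 | 100 | 100 | 0 |
| 0.95 | 95 | 105.3 → 106 | 6 |
| 0.90 | 90 | 111.1 → 112 | 12 |
| 0.80 | 80 | 125 | 25 |
| 0.70 | 70 | 142.9 → 143 | 43 |

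If decisions are independent, the chance that all 100 approve is *a* to the power 100: 0.99^100 = 0.37 and 0.95^100 = 0.006. So if approval really is a later step, some shortfall is likely. I give no power figure, because any such figure would need an invented effect size and the intervention is delivered in groups.

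**Which row applies?** This depends on when approval is obtained, so the passages have to be read together.

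1. The opening paragraph of the protocol presents the study as one in which the culturally adapted intervention is delivered online in groups and its effectiveness measured. Consent to the study is then most naturally consent to an intervention study.
2. The second-stage paragraph puts the study information and this consent before any questionnaire, and so before anyone can be counted.
3. The opening paragraph places the first measurement one week before the intervention. The pre-test is therefore the trial baseline, not a free-standing survey whose respondents are approached again later.
4. The third-stage entry list overlaps itself. It names the inclusion criteria and the screening procedure as two items, although the second stage describes eligibility through that screening. A list that already restates one condition may equally restate consent.
5. The same aim of 100 in both stages is what one would write for a single cohort carried forward.

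On this reading *a* = 1, the first row applies and the two figures agree.

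**The case for a change.** The best case for a change is textual. The third-stage sentence begins with a restriction and sets approval beside the other conditions, which would be redundant if approval were already in hand. The path from K10 through SCID-5 to the pre-test names no agreement to eight weeks of group sessions or to random assignment. The consent sentence leads only to completing questionnaires. Who counts toward a recruitment stop is a protocol matter that a statistical analysis plan would not usually settle, and the repair would take a sentence or two.

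Part of this stands. The protocol does not say outright when approval is obtained, and a sentence to that effect would be clearer. The rest does not carry the point. The wording of the consent form, which would settle the matter, is not part of the text under review, so its silence cannot be counted against the plan. The lower acceptance rates have no support in the document: people reaching the count have consented and completed two screening steps, and controls can receive the intervention after the last measurement, which removes one reason to decline. Leaving replacement and reopening unmentioned in so short a protocol is an omission of logistics, not an error.

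**Conclusion.** The concern does not call for a change. On the reading the protocol best supports, consent precedes the count, 100 people enter random assignment and the shortfall is zero. If approval is in fact asked later, the trial randomises somewhat fewer than 100: 95 at an assumed 95% acceptance, 70 at an assumed 70%. The comparison between arms stays unbiased in either case, because refusal comes before assignment. Both figures are worded as aims, and no power statement or sample-size derivation in this document depends on reaching exactly 100, so a smaller number contradicts nothing the plan claims.

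Saying when approval is obtained, or describing the third-stage aim as an upper limit, would tidy the wording without altering the design. Recruiting 6 to 43 further eligible people to cover an assumed refusal rate would mean more screening and enrolment, with no missed figure in the document to justify it. This conclusion rests on reading consent to the study as consent to the intervention study that the opening paragraph describes. The consent text itself was not available to confirm it.

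### The K10 effectiveness test is stated as a comparison of change from baseline with no baseline covariate; adding the pre-test K10 would gain precision at almost no cost

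*Protocol*

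**What the plan says.** The data analysis paragraph, after the description of the fourth stage, has one sentence on how effectiveness is tested: by "comparing the changes in the scores of primary outcome measure (K10" and of the secondary scales (PHQ-9, GAD-7, PCL-5, WHO-5), "between the baseline and follow-up measure". The sentence before it names only the software: "The data will be analyzed by using a statistical package called IBM SPSS 26.0". No model or covariate is stated, and no other part of the protocol mentions baseline adjustment.

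A baseline is collected. Outcomes are "measured three times (one week before the intervention, one week after the intervention and one month after the post-measurement", and the second stage describes a pre-test taken after screening. K10 is also used earlier to select participants: "They will first fill the Kessler Psychological Distress Scale (K10) as a first step of screening". In the third stage participants are randomised, "assigned to the care as usual and care as usual/intervention groups". On size, the third stage says: "The aimed participant number for this stage is 100". The protocol does not say how that number was reached.

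**The concern.** The sentence commits to a quantity, the change in K10, and read as written it leads to a t-test on change or the equivalent two-occasion group-by-time test. Such a test subtracts the whole baseline value, as if each point of baseline K10 carried over as exactly one point at follow-up. The schedule puts about 14 weeks between the two measurements (1 week + 8 weeks + 1 week + 1 month), so a slope below 1 is plausible, although the documents do not give it.

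Two things are at stake. First, precision: with only 100 participants, unnecessary variance costs power. Second, chance imbalance: if the arms differ at baseline by D, the change-score estimate moves by (1 − slope) × D in the opposite direction, so an arm that happens to start worse looks better. Baseline adjustment removes that shift. Bias and type I error are not at stake, because randomisation protects both analyses.

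**Working it through.** The protocol gives no power figure to reproduce: 100 is stated without alpha, power, effect or SD. The check therefore compares the two analyses.

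**Inputs.** From the protocol: two randomised arms, total 100, K10 change from baseline to follow-up. Assumed, because not stated: 50 per arm, two-sided 0.05, effect 0.5 SD, equal SDs at both occasions (so the slope equals the correlation r), full retention and independent participants.

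**Formulas** (X = pre-test, Y = follow-up, b = slope of Y on X within arm):
- Var(Y − X) = residual variance + (1 − b)² × Var(X). The second term is the excess over the adjusted analysis. It is never negative and is zero only at b = 1.
- With equal SDs in units of 1 SD: change 2(1 − r); adjusted 1 − r². The ratio adjusted/change is (1 + r)/2.
- Estimating the slope multiplies the adjusted variance by 1 + 1/(N − 4) = 1 + 1/96 = 1.0104.
- SE of the arm difference = √(2 × variance / 50). Power is from the noncentral t with 98 df (change) or 97 df (adjusted).

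**Example, r = 0.5.** Change: variance 1.00, SE = √(2 × 1.00/50) = 0.200, effect/SE = 2.50, power 70%. Adjusted: variance 0.75 × 1.0104 = 0.758, SE = √(2 × 0.758/50) = 0.174, effect/SE = 2.87, power 81%.

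| r | Var, change | Var, adjusted | Ratio | Power, change | Power, adjusted | N for change to match adjusted on 100 |
|---|---|---|---|---|---|---|
| 0.3 | 1.40 | 0.919 | 0.66 | 55% | 73% | 152 |
| 0.5 | 1.00 | 0.758 | 0.76 | 70% | 81% | 132 |
| 0.6 | 0.80 | 0.647 | 0.81 | 79% | 87% | 124 |
| 0.7 | 0.60 | 0.515 | 0.86 | 89% | 93% | 116 |
| 0.8 | 0.40 | 0.364 | 0.91 | 97.5% | 98.4% | 110 |

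With equal SDs the adjusted analysis is the more precise for every r below about 0.98. The lost degree of freedom moves the critical t only from 1.9845 to 1.9847.

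**Simulation.** With 8,000 trials per r and 50 per arm, a t-test on change against ANCOVA gave power of 56.0% vs 73.9% (r = 0.3), 69.3% vs 81.1% (0.5), 89.2% vs 93.3% (0.7) and 97.4% vs 98.4% (0.8). Mean error was below 0.004 SD for both.

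**Chance imbalance.** The SE of the baseline difference is √(2/50) = 0.2 SD. An imbalance of that size shifts the change-score estimate by (1 − r) × 0.2 = 0.14, 0.10, 0.06 and 0.04 SD at r = 0.3, 0.5, 0.7 and 0.8. In the simulation, estimation error regressed on the imbalance had slopes of −0.70, −0.50, −0.31 and −0.21 for change, and between −0.01 and 0.002 for ANCOVA.

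**Other assumptions** (power by normal approximation, without the slope cost):
- 20% attrition (40 per arm): 47% vs 65% at r = 0.3, 61% vs 73% at 0.5, 82% vs 88% at 0.7, 94% vs 96% at 0.8.
- Clustering in the intervention arm (assumed groups of 10, ICC 0.05, factor 1 + 9 × 0.05 = 1.45) at r = 0.5: 62% vs 74%.
- Baseline SD 0.8 of follow-up SD: the variance ratio, slope cost included, is 0.79, 0.90 and 0.99 at r = 0.3, 0.5 and 0.7. At r = 0.5 the variances are 1 + 0.64 − 2 × 0.5 × 0.8 = 0.84 and 0.75, so effect/SE is 0.5/√(2 × 0.84/50) = 2.73 vs 0.5/√(2 × 0.75/50) = 2.89, and power about 78% vs 82%.
- Follow-up SD 0.8 of baseline SD, r = 0.5: the ratio falls to 0.57, a larger gain.
- Worst case found (baseline/follow-up SD 0.7, r = 0.7, slope exactly 1): ratio 1.01.

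**The case against.** The strongest reply is that this belongs in a SAP. Comparing changes names a quantity, not an estimator. K10 change can itself be analysed with pre-test K10 as covariate, and that gives the same treatment effect and standard error as adjusting follow-up K10. On that view the sentence is silent on adjustment and does not rule it out. This stands in part: the accurate statement is that no adjustment is stated, and a SAP that was not available for this review may provide it. It does not dispose of the point. This is the protocol's only description of the test, it specifies the quantity compared, and its plain reading is the less efficient analysis.

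A second reply is that the size is wholly assumed and that equal SDs may flatter the fix. Entry requires a screening K10 above 15 and no DSM-5 diagnosis, which could narrow the baseline spread relative to follow-up. This also stands as a limit: at a baseline/follow-up SD ratio of 0.8 and r = 0.5, the gain is about 4 power points instead of 11 or 12. The opposite SD pattern would enlarge it. The uncertainty is over how much is gained; the most that adjustment was found to cost is 1% of variance.

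**Conclusion.** The concern holds, as a matter of efficiency and not of validity. As written, the primary comparison is an unadjusted change score that is less precise than a baseline-adjusted comparison unless the slope is at or very near 1. With equal SDs and the other assumptions above, the gain is material for correlations up to about 0.6 (8 to 18 power points between 0.6 and 0.3) and about 1 point at 0.8. It is smaller if the baseline SD is below the follow-up SD. Attrition and clustering change the absolute power but not the direction. Because correlation, SDs, effect size, allocation ratio and retention are all undocumented, none of these figures is a forecast for this trial.

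**What to change.** State that the arms are compared on follow-up K10, or on K10 change, with the pre-test K10 as covariate, by ANCOVA or a mixed model. Specify the pre-test K10, not the screening K10, because K10 is explicitly named only at screening and its place in the pre-test is implied. Apply the same rule to PHQ-9, GAD-7, PCL-5 and WHO-5, each with its own pre-test value. If a SAP already specifies this, align the protocol sentence with it. Naming the covariate before outcome data are seen also removes any later choice between adjusted and unadjusted results.

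The cost is one sentence and one degree of freedom per analysis. No new data are needed, and the planned software fits these models.

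### Does the mediation analysis fail because the protocol gives no measurement occasion for the three mediator scales?

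*Protocol*

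**What the plan says.** The protocol is a short narrative in four stages that ends with a paragraph on data analysis.

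- **Opening paragraph.** The survey and interview are to cover distress, diagnosis, "depression, anxiety, traumatic stress and well-being levels of the participants in addition to the COVID-19 related factors and demographic variables". It then says that "psychological problems and the well-being of the participants will be measured three times": a week before the intervention, a week after it, and a month after that second measurement.
- **Second stage.** The K10 is named as the first screening step. The survey content is again described by topic, without mention of hope, emotion regulation or acceptance.
- **Third stage.** "Two other measurements will be taken about psychological problems and well-being at one week after the intervention (post-test"), with a follow-up one month later. The target is 100 randomised participants.
- **Data analysis paragraph.** Effectiveness is judged on "changes in the scores of primary outcome measure (K10) and secondary outcome measures (PHQ-9, GAD-7, PCL-5, WHO-5) between the baseline and follow-up measure". The next sentence announces the mediation analysis: "Mediation analyses will be conducted to explore the mechanisms of change by using the Dispositional Hope Scale", followed by the names of the Emotion Regulation Questionnaire and the Acceptance and Action Questionnaire-II. The three mediator scales appear nowhere else, and no occasion is attached to them.

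**The concern.** Mediation needs a mediator score taken after allocation, and it is more convincing when that score comes before the outcome it is meant to explain. The sentence on effectiveness names five scales and two occasions. The sentence on mediation names three scales and no occasion, and the accounts of survey content leave out all three constructs. A strict reader could therefore doubt that the mediators are collected after the intervention at all.

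The choice of questionnaire at each visit is settled when data are collected. If the mediators were missing from the post-test survey, no later modelling decision could make up for it, and the stated aim of exploring mechanisms would be lost.

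**Working it through.** The protocol gives no figure on this point, so there is none to reproduce. The check is to compare the text on each scale with what mediation requires.

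**1. What is tied to which occasion**

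| Scales | Screening, by name | Baseline and follow-up, by name | Post-test, by name | Construct tied to all three occasions |
|---|---|---|---|---|
| K10 | yes | yes (analysis sentence) | no | yes |
| PHQ-9, GAD-7, PCL-5, WHO-5 | no | yes (analysis sentence) | no | yes |
| Three mediator scales | no | no | no | no |

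On baseline and follow-up the count is 5 of 5 outcome scales against 0 of 3 mediators. That link comes from a sentence about which scores will be compared, which is not a visit schedule. On the post-test, the occasion that matters most for mediation, the count by name is 0 of 5 against 0 of 3. The outcome scales reach the post-test only through general words for what is measured. Four of the five outcome scales are, like the mediators, named once only and in the same closing paragraph. The real difference is that the outcome constructs appear in the summaries and the mediator constructs do not.

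**2. What each possible schedule would allow**

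Let *a* be the effect of allocation on the mediator and *b* the association of the mediator with the outcome given allocation. The mediated effect in a linear model is *a* × *b*.

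- *Pre-test only.* Randomisation makes the expected arm difference in a pre-test score zero, so *a* = 0 and *a* × *b* = 0 whatever *b* is. Mediation could not be studied.
- *Pre-test and follow-up only.* *a* can be estimated, but mediator and outcome change over the same interval, so their order is unknown.
- *Pre-test and post-test, with or without follow-up.* *a* can be estimated at post-test, and *b* can relate the post-test mediator to the outcome one month later. The order is right.

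**3. Which schedule the text supports**

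None is stated and none is excluded. The summaries list topics without claiming to be complete. The first schedule is the only one that defeats the analysis, and no passage suggests it. It also sits badly with the stated purpose: "Mediation analyses will be conducted to explore the mechanisms of change". That sentence directly follows one about changes in scores, in a design with three measurements, two of them after allocation. The natural reading is that the mediators belong to the repeated surveys.

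**4. What would be left to decide**

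The pairing of mediator and outcome occasions, adjustment for pre-test values, and whether to adjust for post-test K10 are modelling choices. They commonly belong in a statistical analysis plan, which may exist but is not at hand.

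**The case for a change.** The strongest case for a change is that timing of administration is protocol content. An analysis plan can choose a model but cannot create a post-test score, the omission cannot be repaired once the post-test has passed, and a single line would remove the doubt. The protocol also describes measurement content by occasion in several places and each time leaves out the only instruments that serve one of its announced analyses.

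The factual part stands: the occasions are not given, and unrecorded data cannot be recovered. The inference to a flaw does not. The argument needs the scales to be absent from the post-test survey, and the only support for that is their absence from summaries that also name none of the five outcome scales at post-test. Investigators who select three process measures to study change can be expected to give them more than once. Simulated detection rates under assumed coefficients would not help: the failure under pre-test-only measurement is built in by randomisation, and comparisons between adjusted models concern the analysis plan.

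**Conclusion.** The observation is accurate, but it concerns an unstated detail and not a wrong or contradictory rule. It touches three scales and one exploratory analysis. The primary comparison on K10 and the four secondary comparisons are unaffected, because neither their data nor their analysis uses the mediators.

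This conclusion assumes that the mediator scales are in the pre-test and post-test surveys of both arms, which is the ordinary reading of a three-occasion design meant to explore change. If they were in fact given at pre-test only, the mediation analysis could not be done and the conclusion would reverse for that analysis alone. Stating the visits would be an optional clarification that leaves the design as it is, and the pairing of occasions can be left to the analysis plan. No change to the plan is called for.
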